8. ANALYSIS AND STATISTICAL METHODS

8.1 Statistical Plan

Descriptive statistics will be provided in terms of mean \pm standard deviation (SD) or median and interquartile range interval (IQR) for the continuous variables; and in terms of frequency and percentage (%) or rate for the categorical variables. Group comparisons will be assessed by Student t-test or non-

parametric Mann-Whitney test for continuous variables and Chi-squared test or test for proportion for categorical variables.

The accuracy performances will be evaluated by assessing diagnostic yield (DY), accuracy, sensitivity, specificity, positive predictive value (PPV) and negative predictive value (NPV). Comparison of these metrics will be evaluated by test for proportions for independent samples or by McNemar test for paired samples. Analyses will be performed in both per-patient and per-lesion setting.

Further analyses to assess the predictors of diagnostic performance will involve the application of univariable and multivariable logistic regression models.

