3. STUDY DESIGN

This is an observational, prospective, multicentre study with repeated assessment of VCE (performed according to the standard of care, with a subsequent second reading AI-assisted for research purposes with no commercial intent).

The expected duration of the study is 36 months, with a proposed start date of 01/03/2025. A maximum enrolment period of 24 months is anticipated.

Details on the study design are discussed in the sections below.

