6.2 Secondary Endpoint

- Overall diagnostic accuracy (sensitivity, specificity, PPV, NPV) of AIR and SR for detecting erosions and/or ulcers;
- Small bowel reading time of AIR and SR;
- Miss rate of AIR and SR for detecting erosions and/or ulcers;
- Correlation between VCE findings and clinical data.

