At the site of patient's enrolment, investigators will perform VCE by evaluating the video in standard mode according to the recommendations of the European Society of Gastrointestinal Endoscopy, at 10 frames per second in the small intestine, and 20 frames per second in the esophagus, stomach, and colon. Reference points (first gastric image, first duodenal image, first cecal image) will be manually selected by the reader. The cleanliness level will be assessed as adequate (excellent/good) or inadequate (fair/poor) according to the qualitative scale of Brotz. Inflammatory lesions will be described using the Nomenclature and semantic descriptions defined by Leenhardt et al. in the International Delphi consensus (17), specifically modified for this study to ensure inter-observer agreement in the description of lesions (see **Figure 1**). Lesions will be reported specifying their time of appearance (h: min: s, timing of single frames). In case of multiple inflammatory lesions (>5 per tertile), time of appearance won't be specified and the reader will quantify the pathology burden for every tertile reported as 5-10 or >10 inflammatory lesions, specifying the predominant type of inflammatory lesion). At the end of the reading, readers will also calculate the Lewis score for each video. The Lewis score, used to score the known Crohn disease, split up the small bowel in three tertiles based on transit time, evaluating separately for each tertile the presence of villous edema, ulcerations, and stenosis. The assessment of these parameters is based on number, longitudinal extent and specific characteristics. The final score is the highest value among the

three tertiles (see **Figure 2** for details). A score between ≥ 135 and < 790 indicates mild inflammation; and a score of ≥ 790 signifies moderate-to-severe inflammation (18).

Investigators at the enrolment centre will anonymize the video which will be randomly reallocated to another centre for the second blind reading assisted by AI (i.e., the readers performing the capsule reading in AI mode will not be aware of the results of the first reading in standard mode). The same instructions specified earlier will be applied to the AI-assisted reading, except for the reading speed, limited to 2-5 frames per second.

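### Section 8.1 names no paired test for continuous variables, although small-bowel reading time is recorded on the same video in both reading modes

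*Protocol*

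**What the plan says.** Section 3 describes a study "with repeated assessment of VCE". Section 7 (Video Capsule Reading) gives the mechanism: the enrolling centre reads the video in standard mode, then "will anonymize the video which will be randomly reallocated to another centre for the second blind reading assisted by AI". Every video therefore yields one SR result and one AIR result.

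Section 6.2 lists "Small bowel reading time of AIR and SR" as a secondary endpoint. Section 1 puts a shorter reading time, with yield and accuracy preserved, among the study's aims.

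Section 8.1 has one rule for continuous variables: "Group comparisons will be assessed by Student t-test or non"-"parametric Mann-Whitney test for continuous variables" (the line breaks at the hyphen). For the accuracy metrics, the next paragraph provides for comparison "by test for proportions for independent samples or by McNemar test for paired samples". Section 8.2 sizes the study with a test for correlated proportions.

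**The concern.** The plan recognises pairing for binary outcomes, in both the analysis and the sample size, but not for continuous ones. If 8.1 is followed as written, the two reading times of a video are treated as if they came from unrelated patients.

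This has two consequences. Mann-Whitney compares the two marginal distributions of reading time; it does not address the saving on a given video, which is what a user of the software would want to know. An unpaired t-test ignores the covariance between the two times, so its confidence interval and p-value do not fit the design. Because 8.1 names the tests, a statistical analysis plan that follows it would inherit the mismatch.

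**Working it through.** **Is the design paired by the plan's own figures?** No power figure is given for reading time; the only one is N = 164 for diagnostic yield (Section 8.2). Inputs: AIR 11.5%, SR 9%, both positive 8%, margin M = 0.02, one-sided alpha 0.05, power 80%.
- Discordant cells: 0.115 − 0.08 = 0.035 and 0.09 − 0.08 = 0.010. D = 0.025.
- Variance under the alternative: 0.035 + 0.010 − 0.025² = 0.0444.
- Variance under the null, from the restricted maximum-likelihood cells 0.0397 and 0.0197: 0.0397 + 0.0197 − 0.02² = 0.0590.
- n = [1.645·√0.0590 + 0.842·√0.0444]² / (0.025 + 0.02)² ≈ 164.2.

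This matches the stated 164 to rounding. A formula for independent proportions gives 561 per group. The sample size therefore rests on paired readings.

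**What does ignoring the pairing do to reading time?** Let ρ be the within-video correlation of the two times and k the ratio of the AIR SD to the SR SD. The protocol gives neither, so both are assumptions. With one reading of each kind per video,

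unpaired SE / paired SE = √[(1 + k²) / (1 + k² − 2ρk)].

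| Assumed SD ratio k | ρ = 0.3 | ρ = 0.5 | ρ = 0.7 |
|---|---|---|---|
| 1 (plausible on the log scale) | 1.20 | 1.41 | 1.83 |
| 0.2 (raw scale) | 1.06 | 1.11 | 1.17 |
| 0.107 (raw scale) | 1.03 | 1.06 | 1.08 |

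The value 0.107 is 1 − 0.893: it takes the 89.3% mean reduction cited in Section 1 and assumes that the SD shrinks in proportion to the mean. At k = 0.2 the ratio reaches 1.20 when ρ = 0.8.

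The true size of a nominal 5% unpaired test is 2·[1 − Φ(1.96 × ratio)]. At k = 1 this is about 1.9% / 0.6% / 0.03% for ρ = 0.3 / 0.5 / 0.7. At k = 0.2 it runs from 4.1% (ρ = 0.2) to 1.9% (ρ = 0.8). With negative correlation the error reverses: at k = 1 and ρ = −0.2 the ratio is 0.91 and the size 7.4%.

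**Point estimate.** On complete pairs, the mean of the within-video differences equals the difference of the two means. The t-test estimate is therefore the same either way; only its standard error changes.

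**Power for a small effect.** In 20,000 simulated studies of 164 pairs with equal SDs and a 0.2 SD difference, unpaired versus paired t-test power was 43% vs 57% (ρ = 0.3), 41% vs 72% (0.5) and 38% vs 91% (0.7). This effect is far smaller than the one the documents anticipate, so the figures show the mechanism and do not forecast a loss in this study.

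**The case against.** The strongest objection is that 8.1 never assigns these tests to reading time. Its sentence on group comparisons also covers categorical variables by Chi-squared, so it may be meant for comparisons between groups of patients. The authors clearly know that the readings are paired, so the paired test for reading time might be merely unspecified and left to the statistical analysis plan. That reading is possible. However, 8.1 gives no other method for a continuous variable, and Mann-Whitney has no paired form. The Student t-test could be run as a paired test, but the text does not say so.

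Positive correlation is also not guaranteed. A long transit may lengthen both readings, but the AI mode shows selected images, at a different speed, to a different reader at another centre. The correlation could be low. This limits the size of the error; the mismatch with the design remains.

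Three stronger conclusions might be inferred, and the documents do not support them:
- *That 8.1 estimates the wrong quantity altogether.* This applies to Mann-Whitney only; on complete pairs the t-test's mean difference is unaffected.
- *That the Lewis score comparison is also misanalysed.* Section 7 says that "readers will also calculate the Lewis score for each video", but the score is not an endpoint in 6.1 or 6.2 and no AIR-SR comparison of it is planned.
- *That the reading-time claim could be lost.* The large ratios need equal SDs. On the raw scale the loss is modest, and with a reduction near 89.3% significance would probably not change.

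**Conclusion.** The point holds for reading time. Section 8.1 states a method for continuous variables that does not match the paired design, for an outcome that Section 1 makes one of the study's aims. The size depends on assumed values: the standard error is inflated 1.20 to 1.83 times with equal SDs and correlations of 0.3 to 0.7, but only about 1.03 to 1.20 times on the raw scale with an AIR SD of about 0.1 to 0.2 of the SR SD and correlations of 0.3 to 0.8. The usual direction is conservative. What would be wrong is the interval around the time saved, more than the significance verdict. That 8.1 governs reading time is an inference from the absence of any other continuous method, though a well-founded one. The primary endpoint and N = 164 are untouched. The text should be corrected, but the main result is not at risk.

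**What to change.** Add one sentence to 8.1, for example: *Small-bowel reading time is analysed within video, by a paired t-test on log reading time reported as an AIR/SR ratio with 95% CI, or by the Wilcoxon signed-rank test with the Hodges-Lehmann estimate; the same applies to any other continuous measure compared between the two readings of a video.* State that Student t and Mann-Whitney are kept for comparisons between different groups of patients. The cost is a wording change, with no new data, readers or patients.

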6. AIMS AND ENDPOINTS

6.1 Primary Endpoint

- Non-inferiority of AI-assisted reading (AIR) compared to standard reading (SR) in detecting (diagnostic yield - DY) typical lesions of suspected CD (erosions and/or ulcers and/or stenosis).

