8.2 Sample Size

Sample size calculation is assessed at per-patient analysis based on previous evidence by Xie et al 2022 (14) in which the detection rate of erosions and ulcers (common lesions in suspected Crohn disease) in AI-assisted reading was 11.5%, compared to 9% in standard reading (i.e. a difference of the two proportion around $D=2.5\%$). Considering a non-inferiority one side test for the difference between correlated proportions. with a non-inferiority margin $M= 0.02$, a type I error α of 0.05, a power $1-\beta$ of 80%, a difference of the two proportion $D=0.025$ and a plausible proportion of concordance on positive detection in both AIR and SR of 8%, the sample size needed to establish the non-inferiority of AI-reading with respect to Standard Reading is $N=164$ patients (i.e. 164 VCE). The size will be raised up to $N=180$ in order to take into account a potential dropout rate up to 10%. Details about the sample size computation can be found in Liu, J., et al. (19); and in PASS sample size software documentation at https://www.ncss.com/wp-content/themes/ncss/pdf/Procedures/PASS/Non-Inferiority_Tests_for_the_Difference_Between_Two_Correlated_Proportions.pdf).

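### Section 8.1 assigns diagnostic yield to tests of zero difference, so the stated analysis does not test the 2-point non-inferiority margin of the primary endpoint

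*Protocol*

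**What the plan says.** Protocol section 6.1 gives one primary endpoint: "Non-inferiority of AI-assisted reading (AIR) compared to standard reading (SR) in detecting (diagnostic yield - DY) typical lesions" of suspected Crohn's disease.

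Protocol section 8.1 is the only place that says how diagnostic yield (DY) is compared. One sentence there begins "The accuracy performances will be evaluated by assessing diagnostic yield (DY), accuracy, sensitivity, specificity, positive predictive value (PPV" and ends its list with negative predictive value. The next sentence assigns the tests: "Comparison of these metrics will be evaluated by test for proportions for independent samples or by McNemar test for paired samples". Section 8.1 gives no margin, no one-sided hypothesis and no confidence-limit rule.

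Protocol section 8.2 starts from a different test: "Considering a non-inferiority one side test for the difference between correlated proportions". It sets a margin of 0.02, "a type I error α of 0.05" and 80% power, works per patient, and arrives at N = 164, raised to 180 for dropout.

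Section 7 (Video Capsule Reading) makes the comparison paired. Each video is read in standard mode at the enrolling centre and then, blind to that result, in AI mode at another centre.

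**The concern.** A non-inferiority claim needs a test of the null hypothesis that AIR is worse than SR by at least the margin. McNemar and the two-sample proportion test have a different null, namely that the two yields are equal. A non-significant result from either is not evidence of non-inferiority, and a significant one speaks to superiority or inferiority.

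Followed literally, 8.1 leaves two routes, both poor. One reads absence of a significant difference as non-inferiority, with no control of the rate of false claims. The other asks AIR to be significantly better, for which the trial was not sized. The independent-samples option has a further fault for AIR versus SR: it ignores that both modes read the same videos.

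**Working it through.** **Inputs (section 8.2).** Yield 11.5% for AIR and 9% for SR, both positive 8%, margin M = 0.02, one-sided alpha 0.05, power 80%. The cells follow:

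- AIR-only positive: 0.115 - 0.08 = 0.035
- SR-only positive: 0.09 - 0.08 = 0.010
- Discordant in total: 0.045
- Difference D: 0.035 - 0.010 = 0.025

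**Which test gives N = 164?** For the paired score test,

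N = [(z₀.₉₅ s₀ + z₀.₈₀ s₁) / (D + M)]²

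- s₁² = 0.045 - 0.025² = 0.044375, so s₁ = 0.2107.
- s₀ uses the restricted maximum-likelihood cells under a true difference of -0.02: AIR-only 0.0197 and SR-only 0.0397. Then s₀² = 0.0197 + 0.0397 - 0.02² = 0.0590, so s₀ = 0.2428.
- N = [(1.645 × 0.2428 + 0.8416 × 0.2107) / 0.045]² = 164.2.

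This is the plan's figure. Variants that miss it: Wald variance 136, Wald with continuity correction 178, null variance in both terms 180, score formula at one-sided 0.025 211. The trial was therefore sized for the margin-based score test.

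**What the tests do at N = 164.** The probabilities below come from full multinomial enumeration of the two discordant cells. McNemar is two-sided at 0.05. Total discordance is held at 4.5%.

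| True AIR minus SR | Outcome | McNemar, uncorrected chi-squared | McNemar, exact | Score test: non-inferiority declared |
|---|---|---|---|---|
| -2 points (cells 0.0125, 0.0325) | McNemar non-significant | 79.4% | 88.4% | 3.8% |
| -3 points (cells 0.0075, 0.0375) | McNemar non-significant | 55.5% | 70.8% | – |
| +2.5 points (cells 0.035, 0.010) | McNemar significant for AIR | 31.1% | 19.0% | 84.2% |

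Under the design alternative, the score test shows non-inferiority while exact McNemar is non-significant in 65% of trials.

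**Size needed if superiority were required.** For McNemar, N = (1.96 × √0.045 + 0.8416 × 0.2107)² / 0.025² ≈ 563 pairs. The two-sided independent-samples test has about 11% power with 164 readings per mode and would need about 2310 per mode.

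**Does the form of the paired statistic matter?** Yes. At a true difference of -2 points, one-sided error is:

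| Discordance | Wald | Score |
|---|---|---|
| 4.5% | 6.3% | 3.8% |
| 3% | 8.9% | 3.1% |
| 2.5% | 11.6% | 3.0% |

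The documents propose no Wald test. The comparison only shows why the statistic should be named and not merely described as a paired non-inferiority test.

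**The case against.** The best defence is that the protocol, read as a whole, lets the intended test be recovered. Section 6.1 states non-inferiority, and 8.2, in the same chapter as 8.1, gives the margin, sidedness, alpha, unit of analysis and a methods reference. The sentence in 8.1 is a general one covering six metrics in two settings, and it never says primary analysis. It is also conditional: the independent-samples test is for independent samples, so the paired comparison of AIR and SR goes to McNemar. Nor does the protocol say that a non-significant McNemar will be taken as non-inferiority. The finer details could sit in a statistical analysis plan that is not at hand.

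Part of this stands. The intended test can be inferred from 8.2, the independent-samples test may serve comparisons between different patients, and the false-claim rates describe a misreading that 8.1 permits but does not prescribe.

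It does not remove the point. Section 8.2 offers its test only as the basis of the sample size, whereas 8.1 expressly includes DY among the metrics it assigns to other tests. The favourable reading of the pairing condition still ends at McNemar, which ignores the margin. This is a test stated wrongly, not a detail left for later: an analysis plan that named the right test would contradict 8.1.

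**Conclusion.** The concern holds. The analysis stated for DY and the test behind the sample size are different tests, and only the latter addresses the primary endpoint. With AIR worse by exactly the margin, McNemar finds no significant difference in 79% (uncorrected) to 88% (exact) of trials, while the score test errs in 3.8%. Under the design assumptions, the chance of a positive result falls from 84% with the score test to 31% or 19% with McNemar.

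The +2.5-point figures use the cells of 8.2. Those at -2 and -3 points assume that discordance stays at 4.5%, since the protocol gives no value for those cases. The direction does not depend on this: at -2 points with 2.5% to 3% discordance, McNemar is still non-significant in 64% to 69% of trials (uncorrected), or about 88% (exact). Because the defect touches the only primary conclusion, it must be corrected before analysis.

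**What to change.** Rewrite 8.1 so that it states:

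- **Primary analysis:** per patient, a paired non-inferiority test of DY(AIR) minus DY(SR) at one-sided alpha 0.05, with the restricted-maximum-likelihood score statistic that underlies 8.2.
- **Decision rule:** AIR is non-inferior if the lower one-sided 95% score confidence limit for the difference is above -0.02.
- **McNemar for DY:** only as a superiority test, after non-inferiority has been shown.
- **Independent-samples test:** removed for AIR versus SR. It may stay for comparisons between different patients.

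The cost is wording in 8.1. No extra data or patients are needed: on the plan's own assumptions, N = 164 gives the score test about 80% power by the formula and 84% by enumeration.

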To note, the first reading will always be performed at the centre where the patient is enrolled (not randomized). This choice is made to ensure that patients receive the standard level of care at the centre and have full access to clinical history and medical documents for the physician who ultimately diagnoses the condition.

Comparison and Shared Review

An external researcher will compare the results of standard and AI-assisted readings from all the centres to assess the agreement of the observations reported by both readers. For videos containing less than 5 inflammatory lesions per tertile, the correspondence of reading will be evaluated comparing the type and the timing of the lesions. For videos with diffuse disease and multiple lesions, the correspondence of readings will be evaluated considering the number of lesions category (5-10 or >10 , classified for predominant type) reported in a specific tertile. In case of disagreement (for example, lesions missed by either reader in AIR or SR), an external expert reader (read more than 500 capsules) will review the discordant footage, blind to the source of the videos, open exclusively to the footage being reevaluated.

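### Section 8.1 names an independent-samples test or McNemar for AIR and SR metrics, but neither suits lesions clustered within patients or PPV and NPV from two readings of one video

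*Protocol*

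**What the plan says.** Protocol section 8.1 lists six metrics (diagnostic yield, accuracy, sensitivity, specificity, PPV, NPV) and continues: "Comparison of these metrics will be evaluated by test for proportions for independent samples or by McNemar test for paired samples". The next sentence sets the units: "Analyses will be performed in both per-patient and per-lesion setting". It does not say which test goes with which metric or unit. It names no method for clustered lesions and none for paired predictive values.

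Section 7 sets the data structure. The enrolling centre reads the video in standard mode. The video is then "randomly reallocated to another centre for the second blind reading assisted by AI". Lesions are timed individually up to 5 per tertile; above that only a count category is recorded. Where lesions are few, "the correspondence of reading will be evaluated comparing the type and the timing of the lesions".

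Section 6.2 makes sensitivity, specificity, PPV and NPV secondary endpoints and adds "Miss rate of AIR and SR for detecting erosions and/or ulcers", without stating a unit. Section 8.2 sizes the study per patient: "Considering a non-inferiority one side test for the difference between correlated proportions", with margin 0.02.

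**The concern.** Both named tests assume independent units, and McNemar also needs both readings to be scored on one common set of units. Two secondary comparisons break these conditions.

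- **Per lesion.** One SR reader and one AIR reader, at different centres, see all the lesions of a patient. If a patient's lesions are found more easily in one reading than in the other, the discordant lesions fall in blocks and McNemar understates the variance. An AIR-SR difference could then be declared too often. The independent-samples test ignores the clustering too, and also the pairing.
- **PPV and NPV.** Each is conditional on that reading's own result. AIR-positive and SR-positive videos overlap, so they are not independent samples. They are not the same videos either, so McNemar does not test equality of PPV. The same holds for the negative videos and NPV.

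The two errors run in opposite directions: a false difference per lesion, and a missed real difference in PPV or NPV.

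**Working it through.** **The plan's own figure.** Section 8.2 gives 11.5% AIR-positive, 9% SR-positive and "a plausible proportion of concordance on positive detection in both AIR and SR of 8" per cent. So AIR-only = 11.5 - 8 = 3.5%, SR-only = 9 - 8 = 1%, and both negative = 87.5%. The paired non-inferiority score test has n = (1.645√v0 + 0.842√v1)² / (D + M)².

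- D + M = 0.025 + 0.02 = 0.045
- v1 = 0.035 + 0.010 - 0.025² = 0.044375
- v0 = 2 × 0.03968 - 0.02 - 0.02² = 0.0590, where 0.03968 is the SR-only rate fitted under the null

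This gives n = 164.2, which reproduces N=164. The sizing is paired and per patient, and does not depend on the tests questioned here.

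**(a) Per lesion.** Patients positive on either reading: 11.5 + 9 - 8 = 12.5%, and 164 × 0.125 = 20.5, taken as 20. The other inputs are assumptions, because the protocol gives no intraclass correlation, lesion count or shared fraction. Sensitivity is equal in both readings, with logit 1.4 plus a normal patient effect of SD 1 or 1.5 (intraclass correlation about 0.14 or 0.27). The variance of that effect is split into a part shared by both readings and a part separate for each. The top lesion count is 3 tertiles × 5 = 15. Actual error of uncorrected McNemar at nominal 5% (6,000 replicates per cell):

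| Lesions per patient | SD | Fully shared | 3/4 shared | 1/2 shared | Fully separate |
|---|---|---|---|---|---|
| 1-3 | 1 | 4.1% | 5.4% | 5.9% | 7.0% |
| 1-3 | 1.5 | 4.4% | 6.2% | 6.9% | 9.2% |
| 5 | 1 | 5.4% | 7.1% | 8.5% | 11.5% |
| 5 | 1.5 | 4.6% | 9.0% | 12.3% | 17.1% |
| 1-15 | 1 | 5.1% | 10.2% | 13.0% | 20.5% |
| 1-15 | 1.5 | 5.3% | 14.9% | 22.0% | 30.0% |

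Section 8.1 does not name a McNemar variant. With a partly or fully separate effect, the exact or continuity-corrected test gives about 3-6% at 1-3 lesions, and the exact test about 4.5-15% at 5 lesions. A cluster-adjusted McNemar statistic (sum of the patient differences over the root of their sum of squares) stays near 5% or slightly below in every cell. With so few patients, GEE with an uncorrected sandwich variance rejects 6.3-8.8%. With the variance multiplied by K/(K-2) and a t reference on 18 df it rejects 3.7-5.7%.

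**(b) PPV and NPV.** Counts on the section 8.2 rates at N=164:

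- AIR-positive 164 × 0.115 = 18.9; SR-positive 164 × 0.09 = 14.8; both 164 × 0.08 = 13.1
- AIR-negative 145.1; SR-negative 149.2; both 143.5

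Suppose the predictive value is the same whether one or both readings gave the result. The independent-samples variance of the difference is then proportional to n_A + n_S, and the correct one to n_A + n_S - 2n_both.

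- PPV: 33.62 / (33.62 - 26.24) = 4.6 times too large
- NPV: 294.38 / (294.38 - 287.00) = 39.9 times too large

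That supposition is only one case. The actual error was therefore also simulated at N=164 with a pooled z test, for four assumed scenarios that are not the section 8.2 rates (prevalence / sensitivity / false-positive rate / both positive given disease): 0.10/0.80/0.03/0.70, 0.15/0.75/0.02/0.62, 0.20/0.80/0.05/0.70 and 0.30/0.80/0.10/0.70. They imply 17.5, 21.2, 32.8 and 50.8 positives per reading, from 164 × (prevalence × sensitivity + (1 - prevalence) × false-positive rate). With equal true predictive values and nominal 5%:

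- PPV: 2.6-3.1% if no false positives are shared, 1.2-1.4% if a quarter are, 0.3-0.4% if half are
- NPV: 0.5-0.8%

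**The case against.** The best defence is that section 8.1 is a short list of methods whose wording lets the data structure decide between the two tests. It never assigns the independent-samples test to AIR versus SR, and cluster adjustment is commonly left to an analysis plan, which is not shown here. The first part stands: a reader might infer that the protocol has chosen the independent-samples test for this comparison, and the text does not say so. The rest does not remove the point. The sentence names two tests for metrics that include PPV and NPV, the next sentence extends the analyses to lesions, and whichever test is picked does not fit these two cases.

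Second, the per-lesion inflation depends on the McNemar variant and on inputs the protocol does not give. This stands. At 1-3 lesions per patient the exact or continuity-corrected test largely removes it, and a fully shared patient effect causes none. A reader might take the 20-30% cells as the expected error, but they need up to 15 lesions per patient and a patient effect that is largely or wholly separate for each reading.

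Third, miss rate is not among the six metrics of section 8.1, and section 6.2 gives it no unit. This stands too: the point reaches miss rate only if it is analysed per lesion.

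Fourth, only secondary results are touched, and the PPV/NPV error is conservative. Both are true. They limit the weight of the point but do not make the tests suitable.

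**Conclusion.** The point holds for two secondary comparisons. That neither test fits PPV and NPV follows from the design alone: two readings of one video give overlapping but different positive and negative sets. The size of the resulting conservatism depends on how many false positives the readings share, which the documents do not give. For lesions, both tests ignore clustering. The error of McNemar exceeds 5% only to the extent that detection varies by patient separately for each reading, and its size rests wholly on the assumed lesion count, heterogeneity and shared fraction.

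A reader might infer that the primary result or the sample size is undermined, because diagnostic yield is in the same list. The documents do not support this: section 8.2 plans a paired per-patient non-inferiority test, and N=164 reproduces from it. Nor is McNemar wrong throughout. Per-patient accuracy, sensitivity and specificity each have a common denominator for both readings, so McNemar is sound there as a test of equality. The change should be made, with medium confidence in the sizes.

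**What to change.** In Protocol section 8.1:

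- Remove the independent-samples option for AIR versus SR.
- Compare per-lesion metrics, and miss rate if it is analysed per lesion, by a cluster-adjusted McNemar test or by GEE with a small-sample correction.
- Compare PPV and NPV by a paired predictive-value method (generalised score or relative predictive value), or report them descriptively with patient-level intervals.
- Keep McNemar for per-patient accuracy, sensitivity and specificity.
- State that the primary per-patient yield is tested by the paired non-inferiority test with margin 0.02 on which section 8.2 is sized, since McNemar tests a difference of zero.

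The cost is a few lines of wording and slightly more programming. Per-lesion intervals will usually be wider. The primary endpoint, N=164 and conduct do not change.
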